### **4.4 Clinical Visits**

#### **4.4.1. Visit -1 (inclusion visit)**

##### **4.4.1.1. Visit -1: Inclusion Procedures**

Visit -1 will consist of one consultation, split into two components – a pre-screening phase and (in eligible patients) a post screening further assessment component. A

signed and dated informed consent will be obtained during visit -1, before any screening procedures commence. After giving informed consent, patients will proceed through the study visit as depicted in Figure 1.

**4.4.1.2. Visit -1: Inclusion Assessment**

Patients eligibility will be assessed at the screening visit before any further information / data is / are collected.

**Table 5. Inclusion data collection**

Visit number: -1

Inclusion/Exclusion criteria:
 
 
• Age
 
• Smoking:             
 
– Current status
 
– History (pack years)
 
 
 
• Spirometry:             
 
– FEV1
 
– FEV1/FVC
 
 
 

Information & Informed consent

Clinical assessment (additional to inclusion/exclusion criteria):
 
 
• Comorbidities (physician-diagnosed)
 
• Post-bronchodilator spirometry
 
• History of previous exacerbations/hospitalisations
 
• Respiratory symptoms
 
• Respiratory medications
 
• Medications for comorbidities
 
• COPD clinical phenotype
 
• Mood (PhQ-4)
 

Visit number: -1
Demographic assessment (additional to inclusion/exclusion criteria): 
 
• Sex
 
• Height
 
• Weight
 
• Lifestyle factors: occupation; alcohol use
 

Assessment of COPD Impact 
 
• Sputum 
 
– Absent
 
– Present: colour = white
 
– Present: colour = dark
 
 
 
• Daily physical activity (time walked/day) 
 
– <30 minutes
 
– ≥30 minutes but <60 minutes
 
– ≥60 minutes
 
 
 
• Dyspnea (mMRC score) 
 
– 0–1
 
– 0–2
 
– ≥2
 
– ≥3
 
 
 
• Resucue medication use (SAB) 
 
– Number of times in the last week (0-3; >3)
 
– Number of times a day (0-2; >2)
 
– ≥3
 
 
 

COPD Severity: BODE/BODEx Index (calculated; components captured as part of other assessments outlined)
CAT CCQ

#### 4.1.3. Informed Consent

All patients will be asked to give written informed consent having had sufficient time to review and consider the patient information sheet. A signed and dated informed consent form will be obtained before screening procedures commence.

After informed consent is obtained, patients who are screened will be assigned a permanent identification number such that all patients from each investigational centre are given consecutive identification numbers following their inclusion.

A patient who is screened but not enrolled, e.g. because entry criteria were not met or enrolment did not occur within the specified time, may not be considered for screening again.

#### 4.4.1.3. COPD review

##### *Demographics and life-style*

Demographic information including age, height, weight, date of diagnosis of COPD and occupation, and life-style information including current and past smoking history

and alcohol consumption will be recorded.

### ***Lung Function***

Post-bronchodilator forced expiratory volume in one second (FEV1), percentage of predicted forced expiratory volume in one second (FEV1 % predicted), forced vital capacity (FVC) and percentage of predicted forced vital capacity (FVC % predicted) will be measured.

### ***COPD history in the last 12 months (routine data and patient reported)***

A review of the routine data will also be performed to establish the number of COPD exacerbations (defined as acute course of antibiotics or oral steroids course for COPD or an emergency room attendance or hospitalisation for COPD) recorded in the 12-month period prior to screening visit.

Patients will also be asked the number of times they have had a COPD exacerbation in the 12 months prior to screening visit to confirm events recorded in the routine data.

CAT (total score and individual component responses), EQ5-D and CCQ will be evaluated to enable change in these measures/scores to be evaluated at follow-up visits.

### ***COPD Severity***

In order to assess patients COPD severity at baseline, their BODEx Index Score will be evaluated: BMI, obstruction, dyspnea (breathlessness); exacerbations.

### ***COPD Impact Assessment***

In order to assess patients' degree of COPD impact at baseline, information on sputum (presence and colour), breathlessness (mMRC), daily physical activity (minutes walked/day) and (patient reported) rescue medication use will be recorded.

### ***Co-morbidities***

Current co-morbidities will be identified by diagnostic codes (and or therapy) and will be confirmed by the patient.

### ***COPD and other medications***

A review of COPD and concomitant therapies currently prescribed and used by the patient will be performed to support evaluation of the secondary objective (role of guideline-recommended therapy on COPD control).

#### 4.4.2. Visits 0–3: Baseline and follow-up assessment

In baseline visit (3 months after screening visit) patients will be included in one of the study groups (controlled patients or uncontrolled patients) according definitions. The following data will be collected at the time of each follow-up visit in order to assess disease stability between follow-up visits and disease control at time of each visit.

**Table 7. Follow up visit date capture**

Visit numbers: 0-3 (inclusive)
Time of Visit: Follow-up (3 months; 9 months; 15 months; 21 months)
Information & Informed consent
Clinical assessment (additional to inclusion/exclusion criteria): 
 
• History of previous exacerbations/hospitalisations
 
• Respiratory symptoms
 
• Respiratory medications
 
• Mood (PhQ-4)
 

Assessment of COPD Impact 
 
• Sputum 
 
– Absent
 
– Present: colour = white
 
– Present: colour = dark
 
 
 
• Daily physical activity (time walked/day) 
 
– <30 minutes
 
– ≥30 minutes but <60 minutes
 
– ≥60 minutes
 
 
 
• Dyspnea (mMRC score) 
 
– 0–1
 
– 0–2
 
– ≥2
 
– ≥3
 
 
 
• Rescue medication use (SAB) 
 
– Number of times in the last week (0-3; >3)
 
– Number of times a day (0-2; >2)
 
– ≥3
 
 
 

COPD Severity: BODE/BODEx Index (calculated; components captured as part of other assessments outlined)
CAT
CCQ

 Visit 0 and 3 only

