### 2.3. Secondary objectives

With a view to identifying opportunities to refine the tool to optimize its clinical utility and ability to guide treatment decisions to improve COPD outcomes (reduce disease burden and improve stability) and to identify patients in whom it may be best targeted (in terms of beneficially modifying outcomes and achieving cost efficiencies, a number of secondary objectives will also be evaluated. The secondary objectives of the study will aim to:

- 1) Compare the utility of the COPD Control (as defined) as a tool to identify COPD impact and stability with the CAT and CCQ;
- 2) Evaluate the role of “adequate” (i.e. guideline-recommended) treatment prescribing on COPD control.
- 3) Identify demographic and clinical characteristics associated with COPD control status

[figure not shown]

Table 4. Visit summary

Visit number	-1	0	1, 2 and 3
Time of Visit	Inclusion	Baseline 3 months	9, 15 and 21 months or discontinuation
Inclusion/Exclusion criteria	✓		
Information & Informed consent	✓		
Clinical assessment	✓	✓	✓
Assessment of exacerbations since last visit*	✓	✓	✓
Assessment of clinical status since last visit	✓	✓	✓
CAT/CCQ	✓		
Adverse events		✓	✓

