### **4.3. Outcomes**

#### **4.3.1. Primary outcomes**

The primary study outcome will be measured over the 21-month follow-up period.

The primary outcome of interest will be the difference in (annualized) rates of a composite endpoint (“Mortality, hospitalisations and serious COPD morbidity”) for patients controlled vs uncontrolled at baseline. The composite endpoint is defined as occurrence of any of the following:

- For COPD: unscheduled visits to the physician; emergency room attendance
- An exacerbation of COPD
- All-cause: hospitalization or mortality

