### **9.3.2. Outcome variables**

Outcome variables, captured at each follow-up visit will include:

- Impact:
  - Dysnea (mMRC score)
  - Sputum presence; sputum colour
  - Daily physical activity (minutes walked / day)
  - CAT (total score)
  - CCQ (total score)
  - Impact at time of assessment (High vs Low)
  - Change in impact since prior visit (Y/N)

- Change in impact from baseline (Y/N)
- Stability
  - Exacerbations in the last 3 months (patient-reported and based on clinical records)
  - Change in CAT and CCQ in the last 3 months (where available)
  - Stable (vs unstable) disease at time of assessment (Y/N)
  - Change in stability since prior visit (Y/N)
  - Change in stability from baseline (for visits 2-4; Y/N)
- COPD Control Status:
  - Controlled vs Poorly controlled
  - Change in control since prior visit
  - Change in control since baseline (for visits 2-4; Y/N)
- COPD medications (and cost)
- Mood (PhQ-4)
- Other concomitant medications (and cost)
- Lung function (FEV1, FVC, FEV1/FVC)
- Adverse events:
  - SAEs
  - AEs

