#### **9.3.4. Analysis of secondary outcomes**

Secondary outcomes (EQ5, CCQ, changes in lung function, BODE index) will be analyzed using analysis of covariance (ANCOVA), once assumptions for the convenience of this analysis are confirmed, with baseline values and potential confounding factors as covariates and study group as independent variable (Miller, G. A., & Chapman, J. P. 2001). After, Least square (LS) mean  $\pm$  standard error (SE) will be calculated for variables involving each outcome.

Baseline differences between study groups (controlled and uncontrolled COPD patients) will be performed using the Chi-square test (exact Fisher test with observed frequencies  $< 5$ ) for categorical variables whereas continuous variables were tested using *t* test (U-Mann Whitney test if the variables were not normally distributed). A stepwise multivariate logistic regression model to predict control in COPD patients will be performed. All variables explored in the univariate analyses will be considered in the multivariate model as covariates. A conservative significance threshold of 0.01 was used to determine the qualification of data for entry into or deletion from the model.

Finally, an analysis will be performed to evaluate the cost-utility of patients with controlled (as compared to poorly controlled) COPD using analysis of covariance. Data will be collected from the economic department of each collaborating center.

All tests were two-tailed, and significance was set at 5%. All analyses will be carried out using SPSS version 20, SAS version 9.3 and Microsoft Office EXCEL 2007.

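### The visit tables (4, 5 and 7) conflict with the primary endpoint and section 9: follow-up spirometry, weight, EQ-5D and unscheduled COPD visits are not listed, and the mMRC boxes overlap

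*Protocol*

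**What the plan says.** Section 4.4.2 introduces Table 7 as the data to be collected at each follow-up visit, to judge stability between visits and control at each visit. Its clinical items are "History of previous exacerbations/hospitalisations", symptoms, respiratory medication and PhQ-4. It then lists sputum, walking time, mMRC and rescue-use categories, CAT and CCQ. BODE/BODEx is entered as "calculated; components captured as part of other assessments outlined". Section 4.4.1.3 gives the components: "their BODEx Index Score will be evaluated: BMI, obstruction, dyspnea (breathlessness); exacerbations".

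Other parts of the protocol need more than this:

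- Section 4.3.1 counts, for COPD, "unscheduled visits to the physician; emergency room attendance" in the primary composite.
- Section 4.4.1.3 says "EQ5-D and CCQ will be evaluated to enable change in these measures/scores to be evaluated at follow-up visits".
- Section 9.3.2 opens with "Outcome variables, captured at each follow-up visit will include", and its list includes FEV1, FVC, their ratio and an mMRC score.
- Section 9.3.4 states "Secondary outcomes (EQ5, CCQ, changes in lung function, BODE index) will be analyzed using analysis of covariance" and also plans a cost-utility comparison.

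Table 4, the visit summary, has a row for "Assessment of exacerbations since last visit" at all visits and ticks CAT/CCQ at the inclusion visit only.

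**The concern.** Staff who build an eCRF or run visits will look first to the visit tables. A later analysis plan cannot supply a weight, a questionnaire or an event date that nobody was asked to record.

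Three things are at stake. First, the primary composite would lose one of its named event types whenever such a visit did not also qualify as an exacerbation. Second, BODEx is more than an outcome: it decides which impact thresholds apply (≤4 versus ≥5 points), and control is to be assessed at every visit. Third, the hypothesis in section 2.1 names quality of life, decline in lung function or BODE/BODEx, and costs. These are the outcomes whose follow-up data are missing from the tables.

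**Working it through.** There is no stated figure to reproduce. The check sets the tables against the sections that rely on them, over five visits (−1, 0, 1, 2, 3). Table 5 covers Visit −1 and Table 7 covers Visits 0 to 3.

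**Item by item**

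| Item | Needed by | Table 5 (Visit −1) | Table 7 (Visits 0–3) | Elsewhere |
|---|---|---|---|---|
| Spirometry | 9.3.2, 9.3.4, BODEx | listed | 0 of 4 | 9.3.2 promises it at each follow-up visit |
| Weight/BMI | BODEx | listed | 0 of 4 | no visible passage for follow-up |
| EQ-5D | 9.3.4, cost-utility | not listed | 0 of 4, so 0 of 5 overall | 4.4.1.3 intends inclusion and follow-up; absent from 9.3.2 |
| Unscheduled COPD physician visits | 4.3.1 | not listed | 0 of 4, so 0 of 5 overall | none found |
| CAT/CCQ | stability definition, 9.3.2 | listed | 4 of 4, so 5 of 5 overall | Table 4: 1 of 5 |

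**BODEx.** Of its four components, Table 7 supplies exacerbations and, in coarse form, dyspnea. It supplies neither BMI nor obstruction. The table's remark that the components are captured elsewhere is therefore untrue for two of the four.

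**Events.** Sections 4.4.1.3 and 8.1 both count an emergency room attendance for COPD as an exacerbation, and exacerbations are asked about at every visit. Emergency attendances thus largely reach the composite by that route. An unscheduled physician visit that led to no systemic steroid, antibiotic, emergency attendance or admission does not. Section 5 says patients are not contacted apart from the visits, and the routine-record review in 4.4.1.3 looks only at the 12 months before screening.

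**mMRC.** The boxes are 0–1, 0–2, ≥2 and ≥3. Taking the scale as 0 to 4 (the upper end is an assumption, as the protocol does not state it):

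| Grade | Boxes it fits |
|---|---|
| 0 | 0–1, 0–2 |
| 1 | 0–1, 0–2 |
| 2 | 0–2, ≥2 |
| 3 | ≥2, ≥3 |
| 4 | ≥2, ≥3 |

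Every grade fits two boxes.

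- *All applicable boxes ticked:* three classes can be told apart (0–1, 2, ≥3). This serves both impact cut-offs (0–1 versus ≥2, and 0–2 versus ≥3). It does not separate 0 from 1 or 3 from 4, so the score listed in 9.3.1 and 9.3.2 is not recovered.
- *One box ticked:* 0–2 is compatible with 0, 1 or 2, so impact is undetermined in mild-to-moderate disease. The box ≥2 is compatible with 2, 3 or 4, so impact is undetermined in severe disease.

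**CAT/CCQ.** Stability is defined by change over three months, and patients are grouped at Visit 0, three months after inclusion. A site that followed Table 4 alone would have no second score, so the CAT/CCQ part of that grouping could not be derived.

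**The case against.** A reader might infer that BODEx, lung-function change and cost-utility cannot be computed at all. The documents do not support that. Section 9.3.2 lists lung function and an mMRC score at each follow-up visit, so lung-function change is available if sites follow it. Section 4.4.1.3 clearly intends follow-up EQ-5D, and 9.3.4 says the centres' economic departments supply data for the cost-utility analysis. Nothing says, however, that those departments supply utilities, and EQ-5D is the only utility instrument named.

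A reader might also infer that emergency attendances are lost from the composite. They largely are not, because both exacerbation definitions include them.

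The heading in Table 7 that calls its clinical items additional to the eligibility criteria could be read as carrying spirometry forward. Table 4 ticks eligibility at Visit −1 only, and weight is not among the eligibility items in Table 5, so this reading does not close the gap. Severity for the Visit 0 grouping could rest on the inclusion-visit BODEx described in 4.4.1.3. The primary grouping is therefore not shown to fail for want of spirometry or weight.

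Some caution is due about absence. In the copy at hand the bodies of sections 3 and 4.1 are not visible, table numbering runs from 5 to 7, and a footnote mark in Table 4 has no visible note. The single CAT/CCQ tick might be a broken row, although the other blanks in Table 4 fall where one would expect. The eCRF is not shown and may be fuller. These points limit any claim that an item is collected nowhere. They do not remove the conflict between Table 7 and section 9.

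**Conclusion.** The point holds as a conflict between the visit tables and sections 4.3.1, 4.4.1.3, 9.3.2 and 9.3.4. As tabulated, follow-up data do not support BODEx (two of four components unlisted at 4 of 4 visits), lung-function change (0 of 4 visits), EQ-5D and cost-utility (0 of 5 visits), or the unscheduled-visit component of the primary composite (0 of 5 visits).

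The most serious parts are the unscheduled visits and follow-up weight, for which no visible passage provides. Spirometry and EQ-5D are contradictions between table and text. How many composite events would be lost cannot be estimated, because the protocol gives no rate for unscheduled visits without exacerbation treatment. How far the coarse mMRC classes distort BODEx depends on a scoring grid that the protocol does not give.

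**What to change.** Reconcile Tables 4, 5 and 7 with section 9 and the primary endpoint:

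- **Table 7:** add weight and post-bronchodilator spirometry, or delete the lung-function and BODE change outcomes. If they are deleted, trim section 2.1 to match and state which visit's BODEx sets the severity class when control is assessed later.
- **Tables 5 and 7:** add EQ-5D.
- **Follow-up visits:** add a dated count of unscheduled COPD physician visits since the last visit.
- **Table 4:** tick CAT/CCQ at every visit.
- **Tables 5 and 7:** record mMRC as a single grade, 0 to 4.

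The cost is a few extra eCRF fields and one short questionnaire. Spirometry at follow-up is already promised in 9.3.2, so listing it adds no new commitment.

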#### **4.5. SAMPLE SIZE CALCULATION**

Based on a previous pilot study in Spain, approximately 55% of patients with COPD are controlled based on the proposed criteria. The sample size has to be calculated in order to have enough sample of both subgroups (controlled/non controlled) in both levels of severity (mild to moderate and severe to very severe) that will allow to identify differences in outcomes (main outcome: difference in annualised rate of composite outcome). Since there is not previous information about the frequency of the composite outcome, we have performed a conservative approach using the expected frequency of exacerbations in the sample calculation. According to results from ECLIPSE Study, annualised rate of exacerbations in COPD patients in entire sample was 1.2 per person (15). We hypothesize that, in controlled COPD patients, this annual rate can be 40% lower (0.72 per person). Accepting an alpha risk of 5% and a beta risk of 10% in a two-sided test, a total of 285 COPD patients will be necessary to find this annualised incidence ratio difference as statistically significant. It is expected that two thirds of controlled patients have mild to moderate COPD and one third of these have severe to very severe COPD. With an expected drop-out rate of 15%, a total of 328 patients will be enrolled in the study. Sample size has been calculated with !NI2IS macro (SPSS V20).

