### **1.3. Population to be studied**

It is planned that this study will enroll no fewer than 328 patients with a range of COPD severities, Eligible patients will have spirometry-defined COPD (i.e. post-bronchodilator FEV1/FVC<0.7), be over 40 years' of age, be current smokers or ex-smokers with at least 10 pack-years of smoking exposure and be in a stable clinical state (as judged by the investigator) at point of recruitment.

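### Drop-out is added to 285 by multiplying (328) instead of dividing (336), and the single overall calculation does not support the stated aim of showing differences in both severity levels

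*Protocol*

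**What the plan says.** Section 4.5 opens with an aim: the sample should "have enough sample of both subgroups (controlled/non controlled) in both levels of severity", so that outcome differences can be identified. One calculation follows. Its inputs are:

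- Error rates: "Accepting an alpha risk of 5% and a beta risk of 10% in a two-sided test".
- Reference rate, from an external cohort: "annualised rate of exacerbations in COPD patients in entire sample was 1.2 per person".
- Rate in controlled patients: 40% lower, that is 0.72 per person per year.
- Split, from a pilot study: "approximately 55% of patients with COPD are controlled based on the proposed criteria".

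The result is that "a total of 285 COPD patients will be necessary to find this annualised incidence ratio difference as statistically significant". A severity mix of two thirds mild to moderate and one third severe to very severe is given for controlled patients only, and it enters no figure. The last step is the drop-out allowance: "With an expected drop-out rate of 15%, a total of 328 patients will be enrolled in the study".

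The synopsis repeats 328 as the planned number, and section 1.3 makes it a floor ("no fewer than 328 patients").

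**The concern.** Two statements in section 4.5 do not fit the calculation between them.

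First, the drop-out rate is applied to the number needed, when it should apply to the number enrolled. The enrolment target therefore does not deliver the number the section calls necessary if the expected loss occurs.

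Second, the aim covers both severity levels but the calculation covers only the overall contrast. Control is defined with different thresholds in the two levels, and section 9.3 plans analyses split by baseline severity, so severity-specific results will be produced and read. A reader told that the sample was sized for both levels could take a non-significant result in severe disease as evidence that control status does not matter there, although that level was never sized for the question.

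**Working it through.** **Drop-out step.** Inputs are 285 and 15%, both from section 4.5.

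- The protocol's figure is reproduced by 285 × 1.15 = 327.75, rounded up to 328.
- Enrolment that leaves 285 after 15% loss: 285/(1 − 0.15) = 335.3, so 336. Check: 336 × 0.85 = 285.6.
- What 328 leaves: 328 × 0.85 = 278.8, about 279, which is 6 short.
- Largest loss at which 328 still yields 285: 1 − 285/328 = 13.1%.

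**Effect on overall power.** The protocol does not state the model behind 285, so I used two that come close to it.

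- Rate model: test of the log rate ratio with variance (1/(1.2t) + k)/n_u + (1/(0.72t) + k)/n_c, where t is follow-up in years, k is dispersion, and n_u and n_c are the uncontrolled and controlled numbers at 45:55. At t = 1, k = 0.668 is the value that gives exactly 285 for 90% power. With 279 patients, power is 89.4%.
- First event within one year: proportions 1 − exp(−1.2) = 0.699 and 1 − exp(−0.72) = 0.513. Power is 89.4% with 285 and 88.8% with 279.

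Either way the loss is about 0.6 percentage points.

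**Severity levels.** Of 285, 55% controlled is about 157, split into 104 mild to moderate and 52 severe. The other 128 are uncontrolled, and their severity mix is not given.

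A bound needs no assumption about that mix. If every uncontrolled patient fell in one level, that level would hold at most 104 + 128 = 232 (mild to moderate) or 52 + 128 = 180 (severe). Both are below 285. Taking the larger case in the rate model above:

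- variance = (1/1.2 + 0.668)/128.25 + (1/0.72 + 0.668)/104.5 = 0.0117 + 0.0197 = 0.0314, so the standard error is 0.177;
- 0.511/0.177 − 1.960 = 0.92, which gives power of about 82%, and then the other level has no uncontrolled patients at all.

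So under a calculation that needs 285 for the overall contrast, neither level reaches 90% for the same contrast.

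How far below depends on the assumptions. The ranges here let one third to two thirds of uncontrolled patients be severe:

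| Assumed model | Overall N needed | Power, severe | Power, mild to moderate |
|---|---|---|---|
| Rate model, 1 year, dispersion 0.668 | 285 | 46–57% | 59–75% |
| First event, 1 year | 291 | 45–59% | 54–74% |
| Poisson, 18 months, no dispersion | about 118 | 83–91% | 93–98% |
| Uncontrolled rate 1.79, dispersion 1, 18 months | about 83 | 93–98% | 98–99.8% |

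The last row reads 1.2 as the rate of the whole cohort, so that the uncontrolled rate is (1.2 − 0.55 × 0.72)/0.45 = 1.79. Its overall N is 10.51 × [(1/(1.79 × 1.5) + 1)/0.45 + (1/(0.72 × 1.5) + 1)/0.55]/(ln(0.72/1.79))², about 83.

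**The case against.** The drop-out slip is trivial in size: 8 patients, or 2.4% of 336. Section 1.3 makes 328 a minimum and the synopsis calls it approximate, so enrolling 336 already fits the protocol. Patients who drop out are not wholly lost either. Section 9.1 keeps all entered patients in the intention-to-treat analysis, section 9.3.3 works with rates per person-year, and section 6.2 asks for observations up to withdrawal. Only a loss before Visit 0, when control status is assigned, clearly contributes nothing. All of this stands, and it makes the drop-out point a minor correction. It does not make 328 the right number for the section's own statement.

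On severity, the protocol sets no target power per level, and its primary outcome is the overall comparison. The stratum powers in the table rest on inputs that the protocol does not supply. That also stands: a reader might infer that power in severe disease is about 50%, but the documents do not support a specific figure, because other rates or less dispersion put it above 80% or 90%. Those favourable cases, however, need only about 83 to 118 patients overall, so they do not fit the stated 285.

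A reader might also infer that 285 itself is wrong, since a plain Poisson comparison over one year needs only about 176 to 181. The documents do not support that either: a one-year first-event comparison on the same inputs gives about 281 to 291, depending on the variance formula and allocation. Nor can 18 months from Visit 0 be read in as the assumed follow-up. Section 4.3.1 speaks of a 21-month period, and the first-event match to 285 uses one year.

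**Conclusion.** The point holds in two parts of unequal weight.

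The drop-out allowance is miscalculated: 336, not 328, is needed for 285 after 15% loss. This follows from the protocol's own figures. The consequence is small, as shown above, and does not make the trial materially underpowered for its overall comparison.

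The aim for both severity levels is not backed by the calculation given. This rests on the protocol's figures plus one assumption, that the contrast to be found within each level is the same 1.2 versus 0.72. How much power each level really has cannot be settled from the protocol. The finding is that the 90% claim does not extend to the severity levels; it is not an estimate of how far they fall short.

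**What to change.** - In section 4.5, section 1.3 and the synopsis, either state 336 enrolled, or keep 328 and state about 279 expected evaluable with the corresponding power, which is just under 90%. The sponsor should take that power from the same macro that produced 285.
- In section 4.5, replace the sentence on both severity levels with one such as: the 90% power applies to the overall comparison of controlled with uncontrolled patients; results by severity level are reported as estimates with 95% confidence intervals, and no power is claimed for them.

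The cost is an edit to three places in the text. Keeping 328 requires no further recruitment; choosing 336 adds 8 patients.
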